Furosemide for Accelerated Recovery of Blood Pressure Postpartum: a randomized controlled trial (FoR BP trial)

A randomized, double-blind, placebo-controlled single center investigation of furosemide's effect on postpartum blood pressure control in pregnancies affected by hypertensive disorders of pregnancy

Protocol date: July 19, 2018

NCT#03556761

Furosemide for Accelerated Recovery of Blood Pressure Postpartum: a randomized controlled trial (FoR BP trial)

A randomized, double-blind, placebo-controlled single center investigation of furosemide's effect on postpartum blood pressure control in pregnancies affected by hypertensive disorders of pregnancy

Principal Investigator: [name], MSCE

Assistant Professor

Division of Maternal Fetal Medicine

Department of Obstetrics and Gynecology

[name]

[name]

Sub-Investigator(s): [name] [name]

Clinical Fellow

Division of Maternal Fetal Medicine

Department of Obstetrics and Gynecology,

Study Drug/Study Device: Furosemide (Lasix)

LIST OF ABBREVIATIONS

AE Adverse Event

CTCAE Common Terminology Criteria for Adverse Events

DSMB Data and Safety Monitoring Board

gHTN Gestational hypertension H&P History & Physical Exam

HRPP Human Research Protections Program
HDP Hypertensive disorders of pregnancy

[figure not shown]
HTN Hypertension IV (or iv) Intravenously

PI Principal Investigator
PO per os/by mouth/orally
PPHTN Postpartum hypertension

PR Partial Response

SAE Serious Adverse Event

STUDY SCHEMA

STUDY SUMMARY

Title	Furosemide for Accelerated Recovery of Blood Pressure Postpartum: a randomized controlled trial			
Short Title	FoR BP trial			
Methodology	Double blind, randomized, placebo control design			
Study Duration	20 months			
Study Center(s)	Single-center			
Objectives	To investigate the impact of a short course of furosemide on postpartublood pressure recovery in women with hypertensive disorders of pregnancy (HDP).			
Number of Subjects	385			
Diagnosis and Main Inclusion Criteria	Clinical disease state under study: hypertensive disorder of pregnancy, postpartum with delivery >20 weeks EGA, diagnosis of HDP antepartum, intrapartum and up to within 1 day of delivery			
Study Product(s), Dose, Route, Regimen	Furosemide (Lasix), 20mg, PO, daily			
Duration of administration	5 days			
Reference therapy	Placebo			
Statistical Methodology	Intention to treat analysis, chi-square tests for categorical variables, two-sample t-test for continuous variables			

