2.3 Endpoints

2.3.1 Primary endpoint

- **2.3.1.1** Postpartum hypertension composite outcome, defined as:
 - Persistently elevated blood pressure (≥140/90) at 7 days postpartum OR
 - Additional requirement of antihypertensive agents after randomization

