5.5 Study schedule

Procedure	At Enrollment	Within 1 day of delivery	Postpartum, in house	Postpartum, at home	Up to 10 days after discharge	Postpartum 6 weeks
Inclusion/exclusion and demographics	Х	Х				
Randomization	Х	X				
Start intervention/ placebo		Х				
Intervention/placebo			X	X		
Blood pressure collection	Х		X	X	Х	X
Maternal outcomes						X

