9.2 Data Analyses Plans

To account for the multiple measurements per patient, we will employ repeated measure regression techniques. Measures of relative risk will include 95% confidence intervals. Descriptive statistics will be presented as mean with standard deviation, median with interquartile range, or proportion with 95% confidence interval based on data type and distribution. Comparisons between groups will be performed using a Chi-square or Fisher's exact test for categorical variables and parametric or non-parametric tests for continuous variables, as appropriate. Bivariable analysis will be used to determine variables (risk factors) that are independently associated with PPHTN. Intention-to-treat analyses will be conducted such that all patients with available follow-up measures will be included in the analysis. Blood-pressure measurements after randomization will be compared between groups with the use of a mixed-effects logistic-regression model, which will account for participants having different numbers of observations over a varying time span. Statistical analyses were conducted in SAS, version 9.4 (SAS Institute, Cary, NC). Two-tailed P values of <0.05 will be considered statistically significant.

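### The mixed logistic model for repeated blood-pressure readings has no stated cut-off or model terms, and its conditional odds ratio must not be read as a relative risk; a baseline-adjusted linear mixed model would serve this supportive analysis better

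*Combined protocol and SAP*

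**What the plan says.** Section 9.2 contains four statements that bear on this point.

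- For the repeated readings: "Blood-pressure measurements after randomization will be compared between groups with the use of a mixed-effects logistic-regression model". The reason given concerns unequal follow-up: "which will account for participants having different numbers of observations over a varying time span".
- A general statement: "To account for the multiple measurements per patient, we will employ repeated measure regression techniques". The type of regression is not named.
- On the effect measure: "Measures of relative risk will include 95% confidence intervals". This is tied to no endpoint or model.
- On other comparisons: "Chi-square or Fisher's exact test for categorical variables and parametric or non-parametric tests for continuous variables, as appropriate". The study summary is similar: "chi-square tests for categorical variables, two-sample t-test for continuous variables".

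The primary endpoint in section 2.3.1 is binary. Its blood-pressure component is "Persistently elevated blood pressure (≥140/90) at 7 days postpartum OR" and its other component is a need for additional antihypertensives. None of the endpoints in section 2.3 is a mean blood pressure.

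Pressure is recorded as a vital sign at screening (section 5.1.6), and the row "Blood pressure collection" in section 5.5 is marked at enrolment. Section 5.2 stratifies randomisation by severe features.

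**The concern.** Blood pressure in mmHg is a number, and a logistic model cannot be fitted to it until each reading is classed as above or below a limit. Because the limit is not stated, the analysis cannot be run as written, and a choice made after the data are seen could affect the result. Cutting the readings also costs precision and hides the size of any difference in mmHg.

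The unstated terms matter in this design. Readings are taken every 4 hours in hospital (section 5.3) and at least once a day at home (section 4.5). Women with severe features or a caesarean stay about 3 days. The number and timing of readings therefore depend on severity and length of stay, so day and stratum belong in the model. Baseline pressure is on file and would sharpen the comparison.

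Finally, a mixed logistic model gives a within-woman odds ratio. If a reader takes it for the relative risk mentioned in the same section, the effect will look larger than it is.

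**Working it through.** The plan gives no figure for this analysis, so there is none to reproduce. The check has four steps.

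**1. Which cut-off?** Three are available.

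| Limit | Where it appears |
|---|---|
| 140/90 | primary endpoint (2.3.1); resolution (2.3.2.3) |
| 150/100 | antihypertensive treatment (3.4, 4.3, 5.3) |
| 160/110 | severe hypertension (2.3.2.2) |

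Section 9.2 points to none of them.

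**2. Loss for one reading per woman.** For a normal variable cut so that a proportion p lies above the limit, the efficiency relative to the uncut variable is E = φ(z_p)² / [p(1 − p)]. The 45.6% is the day-7 rate in section 9.1. It stands in for the share of readings above the limit, which the documents do not give.

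- p = 0.456: 0.3965² / 0.2481 = 0.634, a loss of 37%.
- p = 0.30: 0.3477² / 0.21 = 0.576, a loss of 42%.
- p = 0.2736 (45.6% × 0.60): 0.3328² / 0.1987 = 0.557, a loss of 44%.
- p = 0.10, as for a rarer limit: 0.1755² / 0.09 = 0.342, a loss of 66%.

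**3. Loss for k readings per woman.** Assume a constant treatment effect, an equal correlation ρ between any two readings of a woman, and a matching correlation ρ_b between the cut readings, taken from the bivariate normal distribution. Then E_k = E × [1 + (k − 1)ρ] / [1 + (k − 1)ρ_b]. The values of ρ and k are assumptions.

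- p = 0.456, ρ = 0.5 (ρ_b = 0.333), k = 7: 0.634 × 4.0 / 2.998 = 0.846, a loss of 15%.
- The same with k = 20: 0.634 × 10.5 / 7.327 = 0.909, a loss of 9%.
- p = 0.2736, ρ = 0.7 (ρ_b = 0.474), k = 7: 0.557 × 5.2 / 3.844 = 0.753, a loss of 25%.

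For ρ from 0.3 to 0.7, k from 7 to 20 and p from 0.2736 to 0.456, the loss lies between about 9% and 25%. It falls as k grows, because dichotomising adds noise that averages out over readings. A rarer limit would lie outside this range.

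**4. Effect measure.** Read the 40% reduction in section 9.1 as relative, so that the risk falls from 0.456 to 0.456 × 0.60 = 0.2736.

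- Marginal odds ratio: (0.2736 / 0.7264) / (0.456 / 0.544) = 0.3767 / 0.8382 = 0.45.
- Conditional odds ratio: find the two logistic intercepts that, averaged over a normal random intercept, return 0.456 and 0.2736, and take the exponential of their difference. With a random-intercept SD of 1, 2 or 3 (assumed), this gives 0.38, 0.27 or 0.18.

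The same risk ratio of 0.60 could therefore be reported as an odds ratio anywhere from 0.45 down to 0.18.

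**The case against.** The strongest reply is that the trial asks threshold questions. Its aims and endpoints concern elevated pressure, severe-range pressure and time to resolution, so a binary model fits them, and a mean difference in mmHg is a quantity the trial never set out to estimate. Amlodipine is also given to either arm when pressure is high, which pulls the mean pressures together. A mmHg difference would therefore not show the effect of furosemide alone. Both parts stand. They call for careful labelling of the linear model and are a reason to allow a threshold analysis beside it. They do not supply the missing cut-off or terms.

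Three stronger readings are tempting, and the documents support none of them.

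- A reader might infer that about 40% of the information is discarded. That holds for one reading per woman cut near the planned rates. The sentence in section 9.2 describes many readings per woman, and with no cut-off stated, no percentage can be fixed.
- A reader might infer that baseline pressure is left out of the model. Section 9.2 lists no terms of any kind, so the plan is silent and does not exclude it.
- A reader might infer that the plan promises a relative risk and then delivers an odds ratio. The relative-risk sentence is general and can belong to the binary primary composite. The effect measure is unassigned, which is not a contradiction.

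Continuous methods are also not ruled out, since the section allows tests for continuous variables and unnamed repeated-measures regression. Simple two-group tests do not handle repeated readings, however, and the logistic model is the only one named for them.

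**Conclusion.** The point holds as under-specification of a supportive analysis, with a better method available from data already planned. The response, cut-off, baseline, time and stratum terms are not stated, and no analysis is named as the source of the relative risk.

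The cost in precision from dichotomising is about 37 to 42% for a single reading at event rates of 45.6% to 30%, and about 9 to 25% for 7 to 20 readings per woman. These figures rest on normal readings and, for repeated readings, on an equal correlation of 0.3 to 0.7 and a constant effect, with the day-7 rate standing in for the share of readings above the limit. The gap between effect measures is larger: a risk ratio of 0.60 is a marginal odds ratio of 0.45, and the conditional one is lower still.

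It would be wrong to infer that the main result is at risk. The primary endpoint is binary by definition and section 9.1 sizes the trial on a binary rate, so the powered analysis is untouched.

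**What to change.** For the repeated readings, replace the logistic sentence in section 9.2 with a linear mixed model for systolic and diastolic pressure separately. Include arm, postpartum day, arm-by-day, baseline pressure and the severe-features stratum, and report mmHg differences by day with 95% confidence intervals. State that these are differences under the antihypertensive treatment given in both arms. The downside is that such treatment pulls the arms together and will blunt the difference.

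If a threshold analysis is kept, fix its cut-off in advance at the primary endpoint's 140/90, adjust for baseline pressure and stratum, and report a marginal risk ratio, for example from generalised estimating equations with a log link and robust standard errors. In either case, say which analysis yields the relative risk.

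The cost is a few lines of text and standard procedures in the SAS software the plan already names. Pressure, time and stratum are already collected, so no new data are needed.

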10 STUDY MANAGEMENT

10.1 Conflict of Interest

Any investigator who has a conflict of interest with this study (patent ownership, royalties, or financial gain greater than the minimum allowable by their institution, etc.) must have the conflict reviewed by the PI and the IRB. All investigators will follow the University's conflict of interest policy.

10.2 Collection of data

We will record data on each patient regarding their demographics, obstetrical and medical history, labor and delivery admission and any readmission information within 6 weeks postpartum.

10.2.1 Private information

Only the study staff listed on the protocol approved by the Institutional Review Board will have access to individually identifiable private information about human subjects. The only individually identifiable private information about human subjects that will be collected for research purposes is the subject's name and medical record number for the purpose of linking the subject to their unique study identifier.

10.2.2 Data Protection

The individually identifiable private information that will be collected is name and medical record number for the purposes on linking the subject to their unique study number for chart review. We will collect phone numbers as well in order to be able to text with patients in the postpartum period to collect their daily blood pressures. The file linking the study number to the name, medical record number and phone number will be kept in a password-protected file on a secure server. Data will be collected primarily by the research team. The electronic database (REDCap) will be stored behind the institution's firewall in a password-protected file.

10.3 Institutional Review Board (IRB) Approval and Consent

It is expected that the IRB will have the proper representation and function in accordance with federally mandated regulations. The IRB should approve the consent form and protocol.

In obtaining and documenting informed consent, the investigator should comply with the applicable regulatory requirement(s), and should adhere to Good Clinical Practice (GCP) and to ethical principles that have their origin in the Declaration of Helsinki.

Before recruitment and enrollment onto this study, the patient will be given a full explanation of the study and will be given the opportunity to review the consent form. Each consent form must include all the relevant elements currently required by the FDA Regulations and local or state regulations. Once this essential information has been provided to the patient and the investigator is assured that the patient understands the implications of participating in the study, the patient will be asked to give consent to participate in the study by signing an IRB-approved consent form.

Prior to a patient's participation in the trial, the written informed consent form should be signed and personally dated by the patient and by the person who conducted the informed consent discussion.

10.4 Data Management and Monitoring/Auditing

10.4.1 Data Safety and Monitoring Plan

Safety monitoring will be performed periodically by the principal investigator. This will include assessment of accuracy of data recording, assuring de-identification of data, and that there is appropriate locked storage of data material. There will be no planned interim analyses. An advisory board will be created for continual oversight of the project. It will be comprised of faculty members within the department with extensive experience in prospective clinical trials. They will perform periodic reviews of safety data from this study. The DSMB that will be created is attached.

10.5 Adherence to the Protocol

Except for an emergency situation in which proper care for the protection, safety, and well-being of the study patient requires alternative treatment, the study shall be conducted exactly as described in the approved protocol.

10.5.1 Emergency Modifications

Investigators may implement a deviation from, or a change of, the protocol to eliminate an immediate hazard(s) to trial subjects without prior IRB approval.

For any such emergency modification implemented, a IRB modification form must be completed within five (5) business days of making the change.

10.5.2 Other Protocol Deviations/Violations

All other planned deviations from the protocol must have prior approval by the Principal Investigator and the IRB. According to the IRB, a protocol deviation is any unplanned variance from an IRB approved protocol that:

- Is generally noted or recognized after it occurs
- Has no substantive effect on the risks to research participants
- Has no substantive effect on the scientific integrity of the research plan or the value of the data collected
- Did not result from willful or knowing misconduct on the part of the investigator(s).

An unplanned protocol variance is considered a violation if the variance:

- Has harmed or increased the risk of harm to one or more research participants.
- Has damaged the scientific integrity of the data collected for the study.
- Results from willful or knowing misconduct on the part of the investigator(s).
- Demonstrates serious or continuing noncompliance with federal regulations, State laws, or University policies.

If a deviation or violation occurs without prior approval from the Principal Investigator, the ensuing guidelines will be followed:

Protocol Deviations: Personnel will report to any sponsor or data and safety monitoring committee in accordance with their policies. Deviations should be summarized and reported to the IRB at the time of continuing review.

Protocol Violations: Study personnel should report violations within one (1) week of the investigator becoming aware of the event using the same IRB online mechanism used to report Unanticipated Problems.

10.6 Record Retention

Study documentation includes all Case Report Forms, data correction forms or queries, source documents, monitoring logs/letters, and regulatory documents (e.g., protocol and amendments, IRB correspondence and approval, signed patient consent forms).

Source documents include all recordings of observations or notations of clinical activities and all reports and records necessary for the evaluation and reconstruction of the clinical research study.

Government agency regulations and directives require that the study investigator must retain all study documentation pertaining to the conduct of a clinical trial. In all other cases, study documents should be kept on file until three years after the completion and final study report of this investigational study.

10.7 Obligations of Investigators

The Principal Investigator is responsible for the conduct of the clinical trial at the site in accordance with Title 21 of the Code of Federal Regulations and/or the Declaration of Helsinki. The Principal Investigator is responsible for personally overseeing the treatment of all study patients. The Principal Investigator must assure that all study site personnel, including sub-investigators and other study staff members, adhere to the study protocol and all FDA/GCP/NCI regulations and guidelines regarding clinical trials both during and after study completion.

The Principal Investigator will be responsible for assuring that all the required data will be collected and entered onto the Case Report Forms. Periodically, monitoring visits will be conducted and the Principal Investigator will provide access to his/her original records to permit verification of proper entry of data. At the completion of the study, all case report forms will be reviewed by the Principal Investigator and will require his/her final signature to verify the accuracy of the data.

